6-point SMBG values			X				X					6-point SMBG consists of measurements before and 2 hours after each of 3 main meals within the same day. These SMBG profiles will be collected by the participant twice (2 days) within 1 week prior to the assigned visits.
Dispense study intervention and/or injection supplies			X		X	X	X					
Injection training			X									All training should be repeated as needed to ensure participant compliance.
Observe participants inject study intervention			X									Participants should administer their first dose of study intervention at the end of this visit, after other study procedures and randomization.
Participants return study intervention and/or injection supplies					X	X	X	X	X			
Assess study intervention compliance					X	X	X	X	X			
Human chorionic gonadotropin (hCG)	X											Human chorionic gonadotropin (hCG) will be measured at Visit 1 for women of childbearing potential.
Follicle-stimulating hormone (FSH)	X											Follicle-stimulating hormone (FSH) will be measured at Visit 1 for potentially postmenopausal women.
Urine pregnancy test (local)			X		X	X	X	X	X			A local urine pregnancy test will be performed at Visit 3, with the result available prior to randomization and first injection of study intervention, and at additional visits as shown in the schedule, for women of childbearing potential only.
Hematology	X		X				X		X	X	X	
Clinical Chemistry	X		X				X		X	X	X	

	Screening/ Lead-In		Treatment Period							Safety Follow- Up	Comments	
			Treatment Period I				Treatment Period II					
Visit	1	2	3	4	5	6	7	8	9	ET	801	
Week of Treatment	-2	-1	0	2	8	16	26	38	52	ET	56	
Allowable Deviation (Days)	-7~+3	±3		±3	±7	±7	±7	±7	±7		±7	The visit date is determined in relation to the date of the randomization visit (± the allowed visit window).
Lipid panel	X		X				X		X	X	X	
Pancreatic amylase, lipase	X		X				X		X	X	X	
Calcitonin	X		X				X		X	X	X	
Urine chemistry	X		X				X		X	X	X	Urinary albumin and creatinine will be measured.
Urine albumin -to creatinine ratio (UACR)	X		X				X		X	X	X	
eGFR	X		X				X		X	X	X	eGFR: Calculated by the Japanese Society of Nephrology equation
Fasting serum glucose			X		X	X	X	X	X	X		
HbA1c	X		X		X	X	X	X	X	X		
Samples for storage			X				X		X	X		Plasma and serum stored samples. Additional samples may be collected at additional timepoints where required (in the event of severe hypersensitivity reactions such as anaphylaxis). See Section 8.3.3(f) and 8.9.

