5.1. Inclusion Criteria

Participants are eligible to be included in the study only if all of the following criteria apply:

Race and Age

1. Japanese participants aged ≥ 20 years at the time of signing the informed consent.

Type of Participant and Disease Characteristics

2. Patients with T2D for ≥ 6 months according to the World Health Organization (WHO) classification.
3. Treated with stable doses of a single OAM (biguanides, DPP-4i, SU, a-GI, TZD, glinides, or SGLT2i) for at least 8 weeks prior to Visit 1; the dose must be more than or equal to minimum maintenance dose as shown in Section 10.7, Appendix 7. Participants taking DPP-4i must agree to stop taking it at randomization. In case of weekly DPP-4i, it must be stopped 1 week before randomization.
4. Have the following HbA1c result at Visit 1, as assessed by the central laboratory:
 - Participants taking DPP-4i: $\geq 7.5\%$ and $\leq 9.5\%$,
 - Participants taking another OAM: $\geq 8.0\%$ and $\leq 10.0\%$

Weight

5. Stable body weight for at least 8 weeks prior to Visit 1 (not changed by more than 5% in the past 8 weeks);
6. Have a body mass index (BMI) of $\geq 18.5 \text{ kg/m}^2$ and $< 35 \text{ kg/m}^2$ at Visit 1;

Sex

7. Males or nonpregnant females (women of childbearing potential participating must agree to remain on contraception during study period);

Contraceptive use by women should be consistent with local regulations regarding the methods of contraception for those participating in clinical studies.

- a. Female participants:

- Women not of childbearing potential (WNOCBP) may participate in this study and include those who are infertile due to surgical sterilization, congenital anomaly or postmenopausal (see Section 10.4, Appendix 4 for definition details).
- Women of childbearing potential (WOCBP) may participate in this study.
 - WOCBP participating must agree to remain completely abstinent (if this is their preferred and usual lifestyle) or in a same sex relationship (as part of their preferred and usual lifestyle) without sexual relationships with

males, use 2 effective methods of contraception, 1 of which must at least be highly effective (see Section 10.4, Appendix 4) from screening until 4 weeks after the last dose of randomized therapy.

- WOCBP must test negative for pregnancy as indicated by negative serum pregnancy test at screening (Visit 1) followed by a negative urine pregnancy test prior to the first exposure (Visit 3; Section 1.3, SoA).

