6.1. Study Intervention(s) Administered

Participants will be randomized in a 2:1 ratio to receive dulaglutide 1.5 mg and 0.75 mg, respectively, each administered weekly as a subcutaneous injection in participants with T2D who are already taking a stable dose of OAM. Participants will receive the study intervention for 52 weeks.

See the minimum maintenance dose of OAMs in Section [10.7](#), Appendix 7.

ARM Name	0.75 mg Dulaglutide	1.5 mg Dulaglutide
Intervention Name	Dulaglutide	Dulaglutide
Type	Drug	Drug
Dose Formulation	Single-use pen	Single-use pen
Dosage Level(s)	0.75 mg once weekly	1.5 mg once weekly
Route of Administration	Subcutaneous injection	Subcutaneous injection
Use	Comparator	Experimental
Sourcing	Provided centrally by the Sponsor via interactive web-response system (IWRS)	Provided centrally by the Sponsor via IWRS
Packaging and Labeling	Study intervention will be provided in autoinjectors (single-use pens) packaged in cartons to be dispensed. Clinical study materials will be labeled according to country regulatory requirements.	Study intervention will be provided in autoinjectors (single-use pens) packaged in cartons to be dispensed. Clinical study materials will be labeled according to country regulatory requirements.

^a Information provided in this table (dose formulation, sourcing) may change throughout the study.

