8.3.1. Timing and Mechanism for Collecting Events

This table describes the timing, deadlines, and mechanism for collecting events.

Event	Collection Start	Collection Stop	Timing for Reporting to Sponsor or Designee	Mechanism for Reporting	Back-up Method of Reporting
Adverse Event					
AE	signing of the informed consent form (ICF)	the follow-up visit	As soon as possible upon site awareness	AE eCRF	N/A
Serious Adverse Event					
SAE and SAE updates – prior to start of study intervention and deemed reasonably possibly related with study procedures	signing of the ICF	start of intervention	Within 24 hours of awareness	SAE eCRF	SAE paper form
SAE and SAE updates – after start of study intervention	start of intervention	participation in study has ended	Within 24 hours of awareness	SAE eCRF	SAE paper form
SAE – after participant's study participation has ended and the investigator becomes aware	After participant's study participation has ended	N/A	Promptly	SAE paper form	N/A
Pregnancy					
Pregnancy in female participants and female partners of male participants	After the start of study intervention	4 weeks after the last dose of study intervention	Within 24 hours of learning of the pregnancy	SAE eCRF ^a	SAE paper form

Event	Collection Start	Collection Stop	Timing for Reporting to Sponsor or Designee	Mechanism for Reporting	Back-up Method of Reporting
Product Complaints					
Product Complaints (PC) associated with an SAE or might have led to an SAE	Start of study intervention	End of study intervention	Within 24 hours of awareness	Product Complaint form ^b	N/A
PC not associated with an SAE	Start of study intervention	End of study intervention	Within 1 business day of awareness	Product Complaint form ^b	N/A
Updated PC information	—	—	As soon as possible upon site awareness	Originally completed Product Complaint form with all changes signed and dated by the investigator	N/A
PC (if investigator becomes aware) ^c	Participation in study has ended	N/A	Promptly	Product Complaint form	

^a Pregnancy itself is not considered to be an AE or SAE. However, to fulfill regulatory requirements any pregnancy should be reported following the SAE process to collect data on the outcome for both mother and fetus.

^b AEs and SAEs that are associated with a product complaint will also follow the processes outlined in Section 8.3.

^c The PC which the investigator becomes aware of after the study has ended.

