10.2. Appendix 2: Clinical Laboratory Tests

- The tests detailed below will be performed by the central laboratory unless designated as local in the SoA and in the table below.
- Local laboratory results are only required in the event that the central laboratory results are not available in time for either study intervention administration and/or response evaluation. If a local sample is required, it is important that the sample for central analysis is obtained at the same time. Additionally, if the local laboratory results are used to make either a study intervention decision or response evaluation, the results must be entered into the eCRF.
- In circumstances where the sponsor approves local laboratory testing in lieu of central laboratory testing (in the table below), the local laboratory must be qualified in accordance with applicable local regulations.
- Protocol-specific requirements for inclusion or exclusion of participants are detailed in Section 5 of the protocol.
- Additional tests may be performed at any time during the study as determined necessary by the investigator or required by local regulations.
- Pregnancy Testing will be performed as detailed in the SoA (Section 1.3).

Investigators must document their review of the laboratory safety results.

Laboratory/analyte results that could unblind the study will not be reported to investigative sites or other blinded personnel.

Clinical Laboratory Tests

Hematology:	Clinical Chemistry:
Hemoglobin	Sodium
Hematocrit	Potassium
Erythrocyte count (RBC)	Chloride
Mean cell volume (MCV)	Bicarbonate
Mean cell hemoglobin concentration (MCHC)	Total bilirubin
Leukocytes (white blood cells [WBC])	Direct bilirubin
Neutrophils	Alkaline phosphatase (ALP)
Lymphocytes	Alanine aminotransferase (ALT)
Monocytes	Aspartate aminotransferase (AST)
Eosinophils	Gamma-glutamyl transferase (GGT)
Basophils	Blood urea nitrogen (BUN)
Platelets	Creatinine
	Creatine kinase (CK) ^a
	Uric acid
	Calcium
	Albumin
Urine Chemistry:	
Albumin	
Creatinine	
Pregnancy Testing (serum, female only):	Lipid Panel:
To confirm menopause	Total Cholesterol
Follicle-stimulating hormone (FSH)	High-density lipoprotein cholesterol (HDL-C)
	Low-density lipoprotein cholesterol (LDL-C) ^c
	Triglycerides
To confirm pregnancy	
Human chorionic gonadotropin	
Pregnancy Test (urine, female only) (local)	Pancreas (exocrine):
	Lipase
	Pancreatic Amylase
Hemoglobin A1c	Calculations:
	Albumin/creatinine ratio (urine)
Fasting serum glucose	eGFR ^b

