Effective contraception	
 • male or female condoms with spermicide • diaphragms with spermicide or cervical sponges • barrier method with use of a spermicide 
 ○ condom with spermicide ○ diaphragm with spermicide, or ○ female condom with spermicide 
Note: The barrier method must include use of a spermicide (i.e., condom with spermicide, diaphragm with spermicide, female condom with spermicide) to be considered effective.

Ineffective forms of contraception	
 • spermicide alone • immunocontraceptives • periodic abstinence • fertility awareness (calendar method, temperature method, combination of above 2, cervical mucus, symptothermal) • withdrawal, • post coital douche • lactational amenorrhea

Males may participate in this trial.

No male contraception is required except in compliance with specific local government study requirements.

Collection of Pregnancy Information

Female Participants who become pregnant

- The investigator will collect pregnancy information on any female participant who becomes pregnant while participating in this study. The initial information will be recorded on the appropriate form and submitted to the sponsor within 24 hours of learning of a participant's pregnancy.

- The participant will be followed to determine the outcome of the pregnancy. The investigator will collect follow-up information on the participant and the neonate and the information will be forwarded to the sponsor. Generally, follow-up will not be required for longer than 6 to 8 weeks beyond the estimated delivery date. Any termination of pregnancy will be reported, regardless of gestational age, fetal status (presence or absence of anomalies) or indication for the procedure.
- While pregnancy itself is not considered to be an AE or SAE, any pregnancy complication or elective termination of a pregnancy for medical reasons will be reported as an SAE.
- A spontaneous abortion (occurring at <20 weeks gestational age) or still birth (occurring at ≥ 20 weeks gestational age) is always considered to be an SAE and will be reported as such.

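### Completers have a scheduled pregnancy test at their exit visit, but early leavers have none at the ET visit, and neither group has one at Visit 801

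*Protocol*

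**What the plan says.** **Windows.** Protocol Section 5.1 (criterion 7) requires contraception "from screening until 4 weeks after the last dose of randomized therapy". Section 8.3.1 ends the collection of pregnancies at "4 weeks after the last dose of study intervention". Section 10.4 (Appendix 4) adds a duty of its own: "The investigator will collect pregnancy information on any female participant who becomes pregnant while participating in this study". That duty includes reporting to the sponsor within 24 hours of learning of the pregnancy, and following it to its outcome.

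**Tests.** Section 10.2 (Appendix 2) sets no times of its own: "Pregnancy Testing will be performed as detailed in the SoA (Section 1.3". In the SoA (Section 1.3), the serum test is done once: "Human chorionic gonadotropin (hCG) will be measured at Visit 1 for women of childbearing potential". The local urine test is done at Visit 3 before the first injection, "and at additional visits as shown in the schedule, for women of childbearing potential only". The row is marked at Visits 3, 5, 6, 7, 8 and 9. The ET and Visit 801 cells are blank.

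**Exit.** Section 4.1 makes ET the visit for anyone leaving the study before Visit 9, with Visit 801 about 4 weeks later. Section 7.1 keeps participants who stop only study drug in the study for all planned measurements.

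**The concern.** The SoA tests women of childbearing potential at Visit 9. No study drug is dispensed at that visit, so this test is not a check before further dosing; in effect it is an exit test. ET is the exit visit for a woman who leaves early, and it has no such test. The documents give no reason for treating the two exits differently. Visit 801, which falls near the end of the 4-week window, has no test for either group.

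At stake is whether an exposed pregnancy is noticed. The reporting and outcome follow-up in Section 10.4 begin only once the site knows of the pregnancy. One that starts after the last scheduled test, and that the woman has not yet recognised, could leave the study unrecorded. This is a matter of participant safety and of complete exposure data, not of efficacy inference.

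**Working it through.** No figure in the plan depends on this point, so there is none to reproduce. The check compares SoA rows and then takes nominal time intervals.

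**1. SoA rows compared** (11 visit columns: 1 to 9, ET, 801)

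| SoA row | Marked at |
|---|---|
| Serum hCG | 1 |
| Urine pregnancy test | 3, 5, 6, 7, 8, 9 |
| Urine chemistry | 1, 3, 7, 9, ET, 801 |
| Hematology | 1, 3, 7, 9, ET, 801 |
| HbA1c | 1, 3, 5 to 9, ET |
| Dispense study intervention | 3, 5, 6, 7 |
| Return study intervention | 5 to 9 |

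The urine chemistry and hematology rows carry ET and 801 marks, so both are sampling visits and both already take urine. The ET column may be incomplete elsewhere too: Section 4.1 has study intervention returned at ET, but the return row is blank there.

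**2. Intervals between scheduled urine tests.** The tests fall at Weeks 0, 8, 16, 26, 38 and 52. The gaps are 8, 8, 10, 12 and 14 weeks.

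**3. Early leavers** (assumed on drug until exit)

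- Longest time without a scheduled test, up to the close of the window = gap + 4 weeks. This gives 8 + 4 = 12 weeks for the shortest gap and 14 + 4 = 18 weeks for the longest.
- With the ±7-day windows at both ends of the longest gap: 14 + 2 + 4 = 20 weeks.
- Average, if leaving times are uniform over 52 weeks (an assumption): mean time since the last test = sum of squared gaps / (2 × 52) = (64 + 64 + 100 + 144 + 196) / 104 = 568 / 104 = 5.46 weeks. Adding 4 gives about 9.5 weeks.

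**4. Completers.** Section 6.1 states: "Participants will receive the study intervention for 52 weeks". The date of the last injection is not given. If it is Week 51, the window closes at Week 55, and 55 − 52 = 3 weeks have no scheduled test. If it is Week 52, the window closes at Week 56, and the gap is 4 weeks.

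**5. Participants who stop only study drug.** They keep their scheduled visits, so the remaining tests up to Visit 9 still apply. The early-leaver gap concerns only those who leave the study itself.

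**6. How common early exit is.** Section 9.2 plans for 10% drop-out: 585 − 528 = 57 participants, of both sexes and all ages. The documents do not say how many would be women of childbearing potential.

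**The case against.** **The passages do not formally conflict.** A reader might infer that the 4-week windows promise testing to their end and that the SoA breaks the promise. They do not. Section 5.1 sets a contraception duty and Section 8.3.1 a reporting window. Where the protocol states its testing requirement (Sections 5.1 and 10.4), it asks for a negative serum test at screening and a negative urine test before exposure. The SoA meets that and adds five on-treatment tests. This objection stands, and it leaves the Visit 801 part close to a matter of preference. It does not explain why completers are tested on exit and early leavers are not.

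**Detection does not rest on volunteered information alone.** A reader might infer that early leavers are never tested again, or that a pregnancy is found only if the woman reports it. The item just before the quoted line in Section 10.2 allows further tests at any time if the investigator judges them necessary or local regulations require them. Early leavers have an examination and an adverse-event review at ET, and are asked back about 4 weeks later. This also stands. A discretionary test is still not a scheduled one.

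**The size is easily overstated.** The 18 weeks is a worst case: a woman on drug who leaves just before Visit 9. Fourteen of those weeks are the ordinary interval between Visits 8 and 9, which every participant has. Expected numbers are also small. Suppose, purely for illustration, that 3% to 10% of the 585 are women of childbearing potential (18 to 59), that contraception fails at 1% a year, and that a urine test takes 2 weeks to turn positive. Completers then have 3 + 2 = 5 weeks uncovered and early leavers 9.5. With 59 women, 53 completing and 6 leaving early, expected conceptions are 53 × 0.01 × 5/52 + 6 × 0.01 × 9.5/52 = 0.06. With 18 women the figure is about 0.02. A tenfold failure rate still gives fewer than one. None of these shares or rates can be taken from the documents as they stand, except that Section 10.4 puts highly effective methods below 1% failure.

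**A test at Visit 801 would not close the window fully.** Under the same 2-week assumption, a Week 56 test misses conceptions after about Week 54, while the window runs to Week 55 or 56.

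**Conclusion.** The point holds as a minor gap in safety scheduling. Completers have a scheduled pregnancy test at their exit visit and early leavers do not, with no reason given. Neither group has one at Visit 801, although contraception and pregnancy collection run to 4 weeks after the last dose. Without a scheduled test, an early leaver can go 12 to 18 weeks at worst, depending on the visit interval, and about 9.5 weeks on average under uniform leaving. A completer goes 3 to 4 weeks. In that time detection depends on participant report or a discretionary test.

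These figures assume nominal visit dates, drug taken up to exit for early leavers, and a last dose at Week 51 or 52 for completers. The blank cells were read from extracted text. The column count agrees with neighbouring rows, but the printed table should be checked. The documents do not give the number of women affected, so no count of missed pregnancies is supported.

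**What to change.** Reconcile the ET cell of the SoA urine pregnancy test row, and the Visit 801 cell if testing there is intended, with the Visit 9 test and with the 4-week windows in Sections 5.1 and 8.3.1. Otherwise, state in the protocol why the two exits differ and that the window after the last scheduled test relies on participant report and discretionary testing. The choice is the sponsor's.

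If cells are added, the cost is a correction to the SoA by amendment and at most one local urine test per affected woman at each such visit. Both visits already collect urine, so no extra visit or sample is needed. If the difference is explained instead, the cost is a sentence of text.

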10.3.1. Definition of AE

AE Definition

- An AE is any untoward medical occurrence in a participant administered a pharmaceutical product and which does not necessarily have a causal relationship with the study intervention. An AE can therefore be any unfavorable and unintended sign (including an abnormal laboratory finding), symptom, or disease (new or exacerbated) temporally associated with the use of a medicinal (investigational) product, whether or not related to the medicinal (investigational) product.

Events Meeting the AE Definition

- Any abnormal laboratory test results (hematology, clinical chemistry, or urinalysis) or other safety assessments (for example, ECG, radiological scans, vital signs measurements), including those that worsen from baseline, considered clinically significant in the medical and scientific judgment of the investigator (that is, not related to progression of underlying disease).
- Exacerbation of a chronic or intermittent pre-existing condition including either an increase in frequency and/or intensity of the condition.
- New conditions detected or diagnosed after study intervention administration even though they may have been present before the start of the study.
- Signs, symptoms, or the clinical sequelae of a suspected drug-drug interaction.
- Signs, symptoms, or the clinical sequelae of a suspected overdose of either study intervention or a concomitant medication. Overdose per se will not be reported as an AE/SAE unless it is an intentional overdose taken with possible suicidal/self-harming intent. Such overdose should be reported regardless of sequelae.
- “Lack of efficacy” or “failure of expected pharmacological action” per se will not be reported as an AE or SAE. Such instances will be captured in the efficacy assessments. However, the signs, symptoms, and/or clinical sequelae resulting from lack of efficacy will be reported as AE or SAE if they fulfill the definition of an AE or SAE.

Events NOT Meeting the AE Definition

- Any clinically significant abnormal laboratory findings or other abnormal safety assessments which are associated with the underlying disease, unless judged by the investigator to be more severe than expected for the participant's condition.
- The disease/disorder being studied or expected progression, signs, or symptoms of the disease/disorder being studied, unless more severe than expected for the participant's condition.
- Medical or surgical procedure (for example, endoscopy, appendectomy): the condition that leads to the procedure is the AE.
- Situations in which an untoward medical occurrence did not occur (social and/or convenience admission to a hospital).
- Anticipated day-to-day fluctuations of pre-existing disease(s) or condition(s) present or detected at the start of the study that do not worsen.

